4.4.3 Subgroup Analyses

Subgroup analyses will be conducted for the primary endpoint, i.e. HBeAg seroconversion at 24 weeks after the end of treatment/principal observation period in ITT population. The follow baseline factors will be included in the subgroup analyses:

- Age groups (<12, ≥12)
- Age groups (<5, ≥5)
- Baseline BSA groups
- Race (Asian, Caucasian, Other)
- Sex
- BMI (<18.5, 18.5 ~ 24.9, >25.0)
- HBV genotype (A, B, C, D, Other)
- Baseline ALT (<5xULN, ≥5xULN)
- Baseline log₁₀(HBV-DNA) (≤median, >median)
- Baseline log₁₀(HBeAg) (≤median, >median)
- Baseline log₁₀(HBsAg) (≤median, >median).

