4.2 INCLUSION CRITERIA

A subject may be included if the answer to all of the following statements is “yes”:

- Male or female subjects aged 3 to < 18 years old at baseline

- Positive HBsAg for more than 6 months
- Positive HBeAg and detectable HBV-DNA at screening (subjects must have > 10,000 copies/mL [$> 2,000$ IU/mL] as measured by PCR)
- A liver biopsy performed within 2 years prior to baseline to confirm the presence of advanced fibrosis or exclude cirrhosis (see [Appendix 1](#)). For subjects with advanced fibrosis, a liver biopsy needs to be performed within 9 months prior to baseline
- Compensated liver disease (Child-Pugh Class A clinical classification; see [Appendix 2](#))
- Elevated serum ALT > ULN but $\leq 10 \times$ the ULN as determined by two abnormal values taken ≥ 14 days apart during the 6 months before the first dose of study drug with at least one of the determinations obtained ≤ 35 days prior to the first dose. Reference range of the testing laboratory should be used
- Signed informed consent from *parent/legal guardian* and willingness of *parent/legal guardian* to abide by the requirements of the study, and signed assent from child if appropriate. *Patients <18 years of age at baseline who are legally adults according to national legislation must consent in their own right.*

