4.3 BASELINE CHARACTERISTICS

4.3.1 Demographics and Baseline Characteristics

Summary statistics will be presented for ITT population for the following demographics, including categorical variables:

Sex, Age group (<5, 5 ~ 12, ≥12), Race, Ethnicity, Body surface area group, Country and continuous variables:

age, weight at baseline, height at baseline, Body Mass Index (BMI), body surface area, weight for age percentile, height for age percentile, weight for age z-score, height for age z-score.

Summary statistics will be presented by ITT population for the baseline characteristics, including categorical factors:

- ALT at Baseline (<1xULN, ≥1xULN ~ <2xULN, ≥2xULN ~ <5xULN, ≥5xULN ~ <10xULN, ≥10xULN)
- HBV genotype
- Family history of HBV
- Mode of HBV acquisition
- Histological diagnosis for fibrosis
- Scale or method used for fibrosis score
- Fibrosis score

and continuous factors:

- HBV-DNA at Baseline
- HBeAg at Baseline
- HBsAg at Baseline
- ALT at Baseline.

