4.4.5 Liver Elasticity Sub-study

Liver elasticity analysis in this section will be performed on those patients enrolled in liver elasticity sub-study⁴. Liver elasticity analysis results will be separately displayed for those patients enrolled in liver elasticity sub-study.

Liver stiffness measure (LSM) and its change from baseline over time will be summarized by treatment group. Graphs of change from baselines of LSM and their corresponding 95% confidence intervals over time will be displayed by treatment group.

Baseline LSM will be summarized by baseline characteristics subgroups, including fibrosis stages, age groups (<12, ≥12) and BMI (<18.5, 18.5 ~ 24.9, >25.0). Box plots of baseline LSM will be displayed by various baseline characteristics subgroups above.

Baseline liver elasticity will also be explored for association with the screening liver biopsy result in these sub-study patients using liver biopsy fibrosis score, using Spearman's correlation coefficients. Confidence intervals of correlation coefficients will be provided as needed.

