4.6.5.1 Definitions

The primary endpoints for assessing treatment effects on growth are actual values at visit and their changes from baseline in (1) height (weight, BMI) for age percentile; (2) height (weight, BMI) for age z-score.

For the current analysis, the gender-specific Centers for Disease Control and Prevention (CDC) Growth Charts for 2000 (Kuczmarski et al. 2000) will be used as reference to calculate the height (weight, BMI) for age percentile and height (weight, BMI) for age z-score.

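### The BMI subgroups use fixed raw cut-offs for ages 3 to under 18, so BMI bands are confounded with age; the bands also leave a small gap up to and including 25.0.

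*SAP*

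**What the plan says.** Protocol 4.2 admits "Male or female subjects aged 3 to < 18 years old at baseline".

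SAP 4.4.3 lists the baseline factors for subgroup analysis of HBeAg seroconversion at 24 weeks after treatment or observation, in the ITT population. One entry is "BMI (<18.5, 18.5 ~ 24.9, >25.0". Another in the same list is "Age groups (<12, ≥12", and there is a second age split at 5 years.

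SAP 4.4.5 plans summaries and box plots of baseline liver stiffness by subgroup, "including fibrosis stages, age groups (<12, ≥12) and BMI (<18.5, 18.5 ~ 24.9, >25.0". The BMI limits are the same. Neither section adjusts them for age or sex.

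For growth, SAP 4.6.5.1 handles BMI differently: gender-specific reference charts "will be used as reference to calculate the height (weight, BMI) for age percentile and height (weight, BMI) for age z-score". The baseline summary in SAP 4.3.1 lists "Body Mass Index (BMI), body surface area, weight for age percentile, height for age percentile" and then weight and height z-scores, so BMI appears there only in raw form.

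SAP 4.4.4 names both age and BMI as candidate factors in the exploratory logistic models.

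**The concern.** The growth section standardises BMI for age and sex. The subgroup sections do not, and they give no reason. If the typical BMI of a 5-year-old differs from that of a 16-year-old, a band such as under 18.5 selects partly on age. Any pattern across bands then mixes age with adiposity.

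This matters for this endpoint because Protocol 1.2 names younger age among the factors that predict interferon response in children with chronic hepatitis B. A higher response in the lowest BMI band could simply be the younger children responding better. The stiffness tables have the same ambiguity.

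There is also a drafting defect. The written bands do not cover every value, so the programmer has to guess where some patients go.

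**Working it through.** **The plan's own figures.** The documents give no BMI distribution, so there is no BMI figure to reproduce. The only stated figure used here is the total of 145 randomised patients (SAP 2.3), and it serves only as a scale. For 32% versus 10%, 2:1 allocation, two-sided 0.05 and 80% power, the usual two-proportion formula gives 126 without continuity correction and 144 with it. At 145 the uncorrected power is 86.6%, consistent with the claim of at least 80%. Nothing below depends on that calculation.

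**Step 1: the gap.** I applied the three bands literally: below 18.5; 18.5 to 24.9 inclusive; above 25.0. The value 24.9 is in the middle band. Values above 24.9 up to and including 25.0 are in none. At one decimal the only unassigned value is 25.0; at two decimals there are ten (24.91 to 25.00). The other numeric splits in SAP 4.4.3 (age, ALT, medians) are exhaustive.

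**Step 2: overlap with age.** All inputs here are assumptions:
- BMI lognormal within age group
- median 15.5 to 17 kg/m² under 12 years and 19 to 20.5 at 12 and over
- coefficient of variation (CV) 10% to 16%
- share of patients under 12 (w) 40% to 60%

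With s = √ln(1 + CV²), the probability of BMI below c at median m is Φ(ln(c/m)/s). Write a and b for the probability of BMI below 18.5 in children under 12 and in those 12 and over. The share of the lowest band that is under 12 is w·a / [w·a + (1 − w)·b].

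- *Weakest overlap* (medians 17 and 19, CV 16%, w = 0.4): s = 0.159, a = Φ(0.532) = 0.703, b = Φ(−0.168) = 0.433. Share = 0.4 × 0.703 / (0.4 × 0.703 + 0.6 × 0.433) = 0.281 / 0.541 = 52%, against 40% of the sample.
- *Strongest overlap* (medians 15.5 and 20.5, CV 10%, w = 0.6): s = 0.0998, a = Φ(1.774) = 0.962, b = Φ(−1.029) = 0.152. Share = 0.577 / (0.577 + 0.061) = 90%, against 60% of the sample.

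Across the scenarios run:

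| Quantity | Range |
|---|---|
| Under 12s with BMI below 18.5 | 70% to 96% |
| Aged 12 and over with BMI below 18.5 | 15% to 43% |
| Share of lowest band aged under 12 | 52% to 90% |
| Share of middle band aged 12 and over | 55% to 97% |
| Patients above 25.0, of 145 | about 0 to 9 |
| Patients in the gap, of 145 | 0.02 to 0.41 |

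In every scenario the under-12s are over-represented in the lowest band; only the degree varies. At 2:1, nine patients in the top band would be about six treated and three control. Scaled to the minimum of 50 sub-study patients, the top of that range is 9 × 50/145, about 3.

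**Step 3: what a change achieves.** Contiguous limits (below 18.5, 18.5 to below 25, 25 and above) leave no value unassigned but keep the link with age. Groups on BMI-for-age z-score or percentile address both problems.

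**The case against.** The strongest reply is that this is one of eleven subgroup entries, with no interaction test or multiplicity claim attached. The stiffness summaries are descriptive; Protocol 8.2.5 rules out formal tests in the sub-study. Correlated factors are normal in a one-at-a-time subgroup list, and the age tables appear in the same list for comparison. The logistic models in SAP 4.4.4 can examine BMI alongside age. All of this stands, and it limits the importance of the point. It does not make the BMI tables themselves interpretable, and SAP 4.4.4 does not cover stiffness.

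A reader might infer more than the documents support:

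- *That the BMI subgroup is largely an age split.* That needs BMI-by-age data. The assumed ranges run from modest overlap to strong.
- *That the top band will be nearly empty.* That is one end of a range of about 0 to 9.
- *That any conclusion from these tables would be wrong.* Within a baseline BMI band, Group A versus Group B is still a comparison of randomised groups. What fails is attributing a difference between bands to adiposity.
- *That the cut-offs are adult ones.* The documents do not say where they come from.

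Two cautions about the remedy also stand. A group below the 5th percentile would hold about 0.05 × 145 ≈ 7 patients in a reference-like sample, roughly five treated and two control, which is as sparse as the present top band. And the BMI z-scores are planned for the Safety population, whereas SAP 4.4.3 uses ITT, so a small extension of the derivation is needed.

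**Conclusion.** The point holds in limited form. Two facts follow from the text alone: raw BMI bands without age or sex standardisation are applied to ages 3 to under 18, and the bands omit values above 24.9 up to and including 25.0. The size of the confounding with age rests wholly on the assumptions in the working; the direction is the same throughout, while the degree is open. The gap is a wording error that probably affects nobody or one patient. The primary test, the sample size and the growth safety analysis are unaffected. This is an inexpensive improvement to secondary tables, not a threat to the trial's main conclusion.

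**What to change.** In SAP 4.4.3 and 4.4.5, replace the BMI bands with exhaustive groups of baseline BMI-for-age z-score or percentile, using the reference in SAP 4.6.5.1. State that the variable is derived for the ITT population and for the sub-study patients. Choose groups that avoid sparse cells: tertiles, or a median split as the same list already uses for baseline HBV-DNA, HBeAg and HBsAg. If raw BMI is kept for any reason, at least make the limits contiguous and say that the bands are not adjusted for age.

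Using the z-score in the SAP 4.4.4 models is optional, since age is already a candidate there.

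The cost is SAP wording and a minor programming extension. Height and weight at baseline are already scheduled for all patients, so no new data are needed.

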4.4.4 Exploratory Analysis

Exploratory logistic regression analyses will be performed to examine the demographics and baseline disease characteristics on the response rate of HBeAg seroconversion at 24 weeks after the end of treatment/principal observation period. Baseline factors including age, sex, race, BSA, BMI, HBV genotype, treatment group and ALT will be examined. Stepwise, backward and multiple logistic regression models will be explored.

4.4.5 Liver Elasticity Sub-study

Liver elasticity analysis in this section will be performed on those patients enrolled in liver elasticity sub-study⁴. Liver elasticity analysis results will be separately displayed for those patients enrolled in liver elasticity sub-study.

Liver stiffness measure (LSM) and its change from baseline over time will be summarized by treatment group. Graphs of change from baselines of LSM and their corresponding 95% confidence intervals over time will be displayed by treatment group.

Baseline LSM will be summarized by baseline characteristics subgroups, including fibrosis stages, age groups (<12, ≥12) and BMI (<18.5, 18.5 ~ 24.9, >25.0). Box plots of baseline LSM will be displayed by various baseline characteristics subgroups above.

Baseline liver elasticity will also be explored for association with the screening liver biopsy result in these sub-study patients using liver biopsy fibrosis score, using Spearman's correlation coefficients. Confidence intervals of correlation coefficients will be provided as needed.

4.5 PHARMACOKINETIC ANALYSES

PK parameters (e.g., clearance [CL/F], volume of distribution [V/F], area under the curve [AUC], maximum concentration [C_{max}], etc.) of PEG-IFN will be estimated using a population PK modeling approach.

All PK parameters will be presented descriptively including arithmetic means, standard deviations, geometric means, coefficients of variation, medians, and ranges.

The relationship between clinical endpoints and PEG-IFN serum exposure may be explored.

The relationship between PK and pharmacodynamics (PD) parameters (e.g., AUC vs. neutropenia) may be explored.

Detailed PK and PK/PD results will be separately planned and presented in a separate population PK analysis report.

4.6 SAFETY ANALYSES

Safety analyses will be performed based on the Safety population.

4.6.1 Exposure of Study Medication

The duration of study drug administration, actual cumulative dose and percentage of actual cumulative dose in planned cumulative dose will be summarized for Group A. A patient listing of study drug administration by center/patient number for Safety Population of Group A will be provided.

⁴ At least 50 consenting/assenting patients at specific sites will take part in the liver elasticity sub-study.

4.6.2 Adverse Events

All adverse events (AEs) will be coded according to the latest Medical Dictionary for Regulatory Activities (MedDRA) version during the study and will be classified by Preferred Term (PT) and System Organ Class (SOC). In primary CSR, AEs from study beginning to 24 weeks after the end of treatment/principal observation period will be reported.

AE summaries will be generated as what follows:

- All AEs by SOC and PT;
- All AEs by intensity⁵;
- AEs by relation to treatment;
- Most frequent AEs with an incidence rate of at least 5% in decreasing order;
- Serious adverse events (SAEs);
- Non-serious AEs of special interests, including: ALT or AST > 3 x baseline value in combination with total bilirubin > 2 x ULN; ALT or AST > 3 x baseline value in combination with clinical jaundice; Suspected transmission of an infectious agent by the study drug
- AEs and lab abnormalities leading to dose modification (Group A);
- AEs and lab abnormalities leading to withdrawal from the study treatment.

Listings of all reported AEs, SAEs, non-serious AEs of special interests, death, AEs and lab abnormalities leading to dose modification, and AEs and lab abnormalities leading to withdrawal from the study treatment, will be provided.

All AEs by SOC and PT will be summarized for age subgroups (<12, ≥12), and age subgroups (<5, ≥5),

4.6.3 Laboratory Data

If more than one visit occurred during a single visit window, then the laboratory data closest to the scheduled visit day will be used. If the two laboratory assessments were equidistant from the scheduled visit day then the later assessment will be used; if there was more than one 'later assessment', that is recorded on the same date and time, then the 'worst' case will be used. The exception is the data within the Baseline visit; in this case, if two or more samples were collected on the day that was closest to the Baseline

⁵ The Division of AIDS (DAIDS) Table for Grading the Severity of Adult and Pediatric Adverse Events should be used to assist in the assessment of intensity

target day, then the earliest sample was selected; if the sample collection time was the same then the worst value was selected.

Laboratory data not reported in International System of Units (SI units) will be converted to SI units before further processing. The reference ranges of each investigator/local laboratory will be used for all parameters.

Listings of laboratory parameters at each visit will be provided by treatment group for Safety population. Summary tables of mean change from baseline of laboratory parameters will be provided (some laboratory parameters will be summarised as multiples of ULN instead of raw values: ALT, AST, alkaline phosphatase (ALP), total bilirubin, gamma glutamyl transpeptidase (GGT)).

Lowest and/or highest values of laboratory data post-baseline will be summarized by treatment group using the DAIDS grading system (except for those laboratory parameters with project-specific grandings provided in [Figure 2](#)). Shift table of the lowest and/or highest post-baseline DAIDS grade for laboratory parameters will be provided (except for those laboratory parameters with project-specific grandings provided). Patients with one or more thyroid function values outside the normal range and with change from baseline meeting pre-specified cutoffs (for free triiodothyronine [FT3] and free thyroxin [FT4], it is increase $\geq 20\%$ or decrease $\geq 20\%$; for thyroid-stimulating hormone [TSH], it is increase $\geq 30\%$) will be summarized and listed by treatment group in Safety Population.

Figure 2 Potentially Clinically Relevant Laboratory Abnormalities for Neutrophil, Lymphocyte, Platelet Counts, Hemoglobin, Triglyceride Concentration and ALT

Parameter	Project Specific	Normal				
Neutrophil Count	≥ 2.0 $\times 10^9/L$	1.5 - <2.0 $\times 10^9/L$	1.0 - <1.5 $\times 10^9/L$	0.75 - <1.0 $\times 10^9/L$	0.5 - <0.75 $\times 10^9/L$	<0.5 $\times 10^9/L$
Lymphocyte Count	≥ 1.5 $\times 10^9/L$	1.0 - <1.5 $\times 10^9/L$	0.5 - <1.0 $\times 10^9/L$	<0.5 $\times 10^9/L$		
Platelet Count	≥ 100 $\times 10^9/L$	75 - <100 $\times 10^9/L$	50 - <75 $\times 10^9/L$	20 - <50 $\times 10^9/L$	<20 $\times 10^9/L$	
Hemoglobin Concentration	≥ 10.0 g/dL	8.5 - <10.0 g/dL	<8.5 g/dL			
Triglyceride Concentration	< 1.13 mmol/L (<100 mg/dL)	1.13 - <2.26 mmol/L (100 - < 200 mg/dL)	2.26 - <3.39 mmol/L (200 - < 300 mg/dL)	3.39-<4.52 mmol/L (300 - <400 mg/dL)	≥ 4.52 mmol/L (≥ 400 mg/dL)	
Serum ALT Activity	<1.25 \times ULN	1.25 – 2.5 \times ULN	>2.5 – 5.0 \times ULN	>5.0 – 10 \times ULN	>10 \times ULN	

Note: ULN = upper limit of normal

Patients with ALT flares (including ALT elevations over 10xULN, ALT elevations larger than 5xULN and less than 10xULN) will be summarized by treatment group based on Safety population.

ALT and neutropenia will be summarized respectively by age subgroups (<12, ≥12), and age subgroups (<5, ≥5).

AEs under infections and infestations for patients with ACTG grade 3-4 lymphopenia or neutropenia will be listed.

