3.1.2.2 Pediatric Dosing of PEG-IFN

This study will use the dose and duration of PEG-IFN established in the NEPTUNE study but modified for pediatric use. Study NR16141 (Schwarz PK/pharmacodynamic [PD] 2006 study) [48] demonstrated adequate levels of PEG-IFN were achieved in a PK/PD study involving 14 children between 2 and 8 years of age infected with CHC when a PEG-IFN dose of 180 μ g/1.73 m² \times BSA was used for 48 weeks of treatment. When pediatric PK data were compared with PK data in adults, it was revealed that mean predicted exposure (area under the curve from 0 hours to a given time point [AUC_{0-t}]) to PEG-IFN in children was 25% to 70% higher than that observed in adults receiving a weekly dose of 180 μ g of PEG-IFN (5667 ng \cdot h/mL vs. a range of mean values from 3334 to 4348 ng \cdot h/mL). There was a high incidence of neutropenia in children compared with adults, which may reflect the higher exposure in children. However, predicted exposures in children were still within the range of individual adult exposures reported (maximum exposure of 11125 ng \cdot h/mL). Decreases in neutrophil counts reversed after the end of treatment, no patients had neutrophil counts less than 0.25 \times 10⁹ cells/L, and neutropenia events were not associated with serious infections or premature withdrawal and were clinically manageable with appropriate dose modification. In addition, dose modifications appeared to have no impact on sustained virological response, indicating that dosing may be slightly reduced to improve exposure-related AEs while maintaining viral response.

The dosing regimen for this study is based on formula dosing of 180 μ g/1.73 m² \times BSA used in the pivotal Phase III HCV pediatric study (NV17424 PEDS-C Study) [41] and in the PK/PD Study NR16141 (Schwarz PK/PD [2006] study) [48]. BSA categories, based on the formula 180 μ g/1.73 m² \times BSA, have been provided to facilitate the calculation of the dose by clinicians and to minimize the risk of dosing errors (Table 1).

Table 1 Pediatric Dosing Regimen

Dose (µg)	BSA Range (m ²)
45	0.51–0.53
65	0.54–0.74
90	0.75–1.08
135	1.09–1.51
180	>1.51

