6.2.1 Stopping Rules

Individual subject treatment with PEG-IFN *must* be stopped in the event of any of the following:

- Severe hypersensitivity reactions (e.g., anaphylaxis, angioedema, bronchoconstriction)
- Severe depression (see also Section 6.2.5.5)
- Absolute neutrophil count $< 0.25 \times 10^9$ cells/L or febrile neutropenia (see also Section 6.2.5.1)
- Platelets $< 25 \times 10^9$ cells/L (see also Section 6.2.5.2)

Discontinuation of individual patient treatment with Pegasys should be considered in the event of any of the following:

- *Evidence of hepatic decompensation (e.g., Child-Pugh Class B or C clinical classification [Appendix 2] or clinical evidence such as ascites or varices) (see also Section 6.2.5.3)*
- *Thyroid abnormalities that cannot be effectively controlled by medication*
- *Hypoglycemia, hyperglycemia, or diabetes mellitus that cannot be effectively controlled by medication*
- *New or worsening visual disorders such as field deficits, decrease or loss of vision*
- *Persistent or unexplained pulmonary infiltrates or pulmonary function impairment*
- *Worsening of psoriatic lesion*
- *Development of autoimmunity, including autoimmune hepatitis*
- *Pregnancy (see also Section 7.2.4)*

In the event of discontinuation from treatment, subjects will be encouraged to remain in the 5-year follow-up period (see Section 4.6.1).

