6.2.5 Specific Dose Reduction Guidance

6.2.5.1 Dose Adjustments for Low Absolute Neutrophil Counts

Absolute neutrophil count ($\times 10^9$ cells/L)	Response
≥ 0.75	None
0.5–0.749	Immediate one-level adjustment and monitor
0.25–0.499	Delay or hold dose until ≥ 1.0 , then resume dose with two-level adjustment and monitor
< 0.25 or febrile neutropenia	PERMANENTLY DISCONTINUE

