7.1.3.1 Follow-up of Abnormal Laboratory Test Values

Clinically significant laboratory abnormalities should prompt a repeat measure no less frequently than every 2 weeks or as clinically indicated, with appropriate clinical

management, until they return to normal or baseline levels, and/or an adequate explanation of the abnormality is found. If a clear explanation is established it should be recorded on the eCRF. See also Section 6.2.5 for specific guidance.

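### SAP Figure 2 has no cut at the protocol's two mandatory blood-count stop limits, so worst-value tables only bound the crossings; 4.6.3 also leaves open whether repeat draws count

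*SAP*

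**What the plan says.** **Stop limits.** Protocol section 6.2.1 lists two count limits at which PEG-IFN must be stopped: "Absolute neutrophil count $< 0.25 \times 10^9$ cells/L or febrile neutropenia" and "Platelets $< 25 \times 10^9$ cells/L". Sections 6.2.5.1 and 6.2.5.2 repeat them as permanent discontinuation. The same sections give different, non-stop actions for neutrophils of 0.25–0.499 and for platelets below 50 but not below 25.

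**Grading.** SAP section 4.6.3 plans that "Lowest and/or highest values of laboratory data post-baseline will be summarized by treatment group using the DAIDS grading system", but "except for those laboratory parameters with project-specific grandings provided in" Figure 2. The shift table carries the same kind of exception. Neutrophils, platelets and ALT are all in Figure 2, so Figure 2 alone sets their classes. Its lowest neutrophil class is <0.5; its two lowest platelet classes are 20 to <50 and <20 (all ×10⁹/L).

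**Choice of draw.** Section 4.6.3 opens with this rule: "If more than one visit occurred during a single visit window, then the laboratory data closest to the scheduled visit day will be used". Ties go to the later draw. Baseline is the only stated exception. SAP section 4.2 leaves the time windows to DAP Module 2.

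**Repeat draws.** Protocol section 7.1.3.1 says that clinically significant laboratory abnormalities "should prompt a repeat measure no less frequently than every 2 weeks or as clinically indicated". Section 6.2.5.3 asks for a repeat ALT in 1 week once ALT reaches 5 × ULN.

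**The concern.** Among count-based findings, the two mandatory stop limits are the most serious ones the protocol names, and the planned worst-value tables have no row for either. A reader of the report could not tell from those tables how many children fell below 0.25 or 25, nor whether the stop rule was followed whenever a limit was crossed.

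The neutrophil limit also figures in the protocol's own dose rationale. Section 3.1.2.2 reports a high incidence of neutropenia in an earlier paediatric study and offers as reassurance that "no patients had neutrophil counts less than" 0.25 ×10⁹/L. Under the planned bands the same statement could be made for this trial only if no child fell below 0.5.

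The draw rule raises a second question. Repeat samples are taken because a value is already abnormal. If the nearest-draw rule is applied before the lowest or highest value is picked, an extreme seen only on a repeat may not reach the lowest/highest-value table, the ALT-flare summary or the thyroid-abnormality summary.

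**Working it through.** The plan states no figure to reproduce here. The check compares cut points and then applies the draw rule to the visit schedule.

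**1. Cut points side by side**

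| Parameter | Protocol limits (6.2.5.1–6.2.5.3) | Figure 2 boundaries | Missing |
|---|---|---|---|
| Neutrophils, ×10⁹/L | 0.75, 0.5, 0.25 (stop) | 2.0, 1.5, 1.0, 0.75, 0.5 | 0.25 |
| Platelets, ×10⁹/L | 50, 25 (stop) | 100, 75, 50, 20 | 25 |
| ALT, × ULN | 5, 10 | 1.25, 2.5, 5.0, 10 | none |

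Figure 2 follows the protocol everywhere except at the two mandatory stops. (A value of exactly 5 × ULN falls in the lower ALT class in Figure 2 and in the upper one in the protocol, which is trivial.)

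**2. Test values sorted into Figure 2**

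- Neutrophils 0.20 and 0.24 (stop) and 0.25, 0.30 and 0.49 (no stop) all fall in <0.5.
- Platelets 20, 22 and 24.9 (stop) and 25, 30 and 49 (no stop) all fall in 20 to <50. Platelets 15 and 19 fall in <20 and are certain crossings.

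**3. What the tables can say.** Let n(band) be the number of children whose lowest post-baseline value is in that band.

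- Neutrophils: 0 ≤ number below 0.25 ≤ n(<0.5).
- Platelets: n(<20) ≤ number below 25 ≤ n(<20) + n(20 to <50).

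The bounds close only when the pooled band is empty. With cuts at 0.25 and 25, both counts are read directly.

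**4. Draw selection, under stated assumptions.** Group A haematology is scheduled at Weeks 1, 2, 4, 8, 12, 18, 24, 30, 36, 42 and 48, then follow-up Week 4 (protocol Table 2). Assume contiguous windows split at the midpoints, and scheduled draws on their target days. Repeats every 14 days between scheduled draws give:

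- three 4-week gaps (4–8, 8–12, 48–follow-up 4) × 1 repeat = 3;
- six 6-week gaps (12–18 through 42–48) × 2 repeats = 12;
- total 3 + 12 = 15.

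Each of the 15 lies 14 days from its nearest target day. Protocol section 5.3 allows ±3 days up to Week 48 and ±7 days afterwards, so each repeat would lose to a scheduled draw taken on time. If the windows were narrow instead, such repeats would fall in no window, and the SAP does not say whether they count. On neither reading does any sentence secure their use in a worst-value output.

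**The case against.** **Other outputs cover part of this.** Stopping is mandatory at these limits, and protocol section 7.1.3 requires an abnormal result that leads to discontinuation to be recorded as an adverse event. SAP section 4.6.2 summarises and lists adverse events and laboratory abnormalities leading to withdrawal from treatment, and likewise those leading to dose modification. Section 4.6.3 adds by-visit laboratory listings. A reader might infer that crossings would be invisible throughout the report; that is not so. What remains missing is a planned count below each limit that includes a child who crossed it and continued.

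**Figure 2 mostly matches.** A reader might infer that it ignores the protocol's action limits. It does not: only two cuts are absent, and platelets below 20 are shown.

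**The draw rule may be only a visit-allocation rule.** It speaks of more than one visit in a window, whereas the lowest and highest values are per-patient extremes with no mention of windows. The thyroid sentence counts patients with one or more abnormal values, which reads naturally as any value. DAP Module 2 and the sponsor's laboratory-data guideline, to which protocol section 8.2.5.3 refers, could settle it. This objection stands in part. It is tempting to conclude that the tables will understate nadirs and peaks, but the SAP does not say whether extremes are taken before or after window selection. It is equally tempting to argue that a 6-week gap holds about three draws at 2-week spacing, so the nadir is lost two times in three. That needs contiguous windows and a nadir equally likely at every draw. No document gives either, and repeats often follow a dose action.

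**The benchmark is background.** It comes from 14 children with hepatitis C, and no planned analysis compares this trial with it. It adds interest to the 0.25 count but does not create the need for it.

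**Conclusion.** The band gap is certain and needs no assumption: neither 0.25 nor 25 is a boundary in Figure 2, and DAIDS grading is switched off for these parameters. The worst-value tables give a range, not a count, for each limit. For neutrophils the lower end is always zero; for platelets it is n(<20). The gap carries over to Group C, whose safety analyses follow section 4.6 (SAP section 4.7).

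The draw-selection point is an ambiguity, not a demonstrated loss of data. As written, the rule excepts only Baseline and can be read to exclude unscheduled repeats from the lowest/highest-value, ALT-flare and thyroid outputs. How often that would matter cannot be calculated from the documents.

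Both should be put right before the primary report, as a matter of clear safety reporting. Neither touches the efficacy analysis.

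**What to change.** 1. In Figure 2, split the lowest neutrophil class into <0.25 and 0.25 to <0.5, and divide 20 to <50 platelets into 20 to <25 and 25 to <50 (×10⁹/L). The number below 25 is then the sum of <20 and 20 to <25.
2. In section 4.6.3, state that the nearest-draw rule applies only to by-visit summaries, and that lowest/highest-value, ALT-flare and thyroid-abnormality outputs use every post-baseline draw, scheduled or not.

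The cost is two extra table rows and a sentence or two of text. No new data are needed, and no clinical rule changes. The extra cuts will not count febrile neutropenia, the other limb of the neutrophil stop, which has to come from the adverse event data.

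There is one small downside. Up to Week 48, Group A has 11 scheduled post-baseline haematology draws and Group B has 4 (Weeks 12, 24, 36 and 48; protocol Tables 2 and 3), and repeats are likely to be commoner in treated children. More draws give more chances to record an extreme. Label the all-draw tables as describing toxicity, not as an unbiased comparison of Group A with Group B.
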